%FEV1	FEV1 expressed as % of predicted normal value
%FVC	FVC expressed as % of predicted normal value
9 HPT	9-Hole Peg Test
AE	Adverse event
AESI	Adverse event of special interest
ALP	Alkaline phosphatase
ALT	Alanine aminotransferase
ARR	Annualized relapse rate
AST	Aspartate aminotransferase
BMI	Body mass index
BP	Blood pressure
bpm	Beats per minute
CDA	Confirmed disability accumulation
CFR	(US) Code of Federal Regulations
CI	Confidence interval
CL	Confidence limit(s)
CRF	Case report form
CRO	Contract research organization
CSR	Clinical study report
CUAL	Cumulative number of combined unique active lesions
DBP	Diastolic blood pressure
DL _{CO}	Diffusing capacity of the lung for carbon monoxide
DMTs	Disease modifying therapies for MS
ECG	Electrocardiogram
eCRF	Electronic case report form
eC-SSRS	Columbia-Suicide Severity Rating Scale (electronic self-rated)

	version)
EDSS	Expanded Disability Status Scale
EMA	European Medicines Agency
EOS	End-of-study
EOT	End-of-treatment
EU	European Union
FAS	Full analysis set
FDA	(US) Food and Drug Administration
FEV1	Forced expiratory volume in 1 second
FSFV	First subject first visit
FSIQ-RMS	Fatigue Symptom and Impact Questionnaire-Relapsing Multiple Sclerosis
FU	Follow-up
FVC	Forced vital capacity
GCP	Good Clinical Practice
Gd+	Gadolinium enhancing
ICF	Informed Consent Form
ICH	International Council on Harmonisation
ICU	Intensive care unit
IDMC	Independent Data Monitoring Committee
INR	International normalized ratio
IRT	Interactive response technology
KM	Kaplan-Meier
LOCF	Last observation carried forward
LSLV	Last subject last visit
MACE	Major adverse cardiovascular events
MedDRA	Medical Dictionary for Regulatory Activities
MI	Multiple imputation
MMRM	Mixed effect model repeated measures
MRI	Magnetic resonance imaging

MS	Multiple Sclerosis
MSFC	Multiple Sclerosis Functional Composite
NAP	Not applicable
NCI	(US) National Cancer Institute
OCT	Optical coherence tomography
PASAT-3	Paced Auditory Serial Addition Test
PBH	Persistent black hole
PD	Pharmacodynamic
PFT	Pulmonary function test
PK	Pharmacokinetic
PPS	Per-protocol analysis set
PTOP	Post treatment observation period
QOL	Quality of life
QT _C	Corrected QT interval
QT _C B	QT interval corrected for heart rate using Bazett's formula
QT _C F	QT interval corrected for heart rate using Fridericia's formula
RMS	Relapsing multiple sclerosis
RRMS	Relapsing-remitting multiple sclerosis
SAF	Safety analysis set
SAP	Statistical analysis plan
SAS	Statistical analysis system
SBP	Systolic blood pressure
SCR	Screened analysis set
SD	Standard deviation
SDMT	Symbol digit modalities test
SDTM	Study Data Tabulation Model
SE	Standard error
SI	Standard international

SOC	System organ class
SOP	Standard operating procedure
SPMS	Secondary progressive multiple sclerosis with superimposed relapses
T25W	Timed 25 Foot Walk
TBIL	Total bilirubin
ULN	Upper limit of the normal range
WHO	World Health Organization
WHODRUG	WHO drug dictionary
WPAI:MS	Work Productivity Activity Impairment: Multiple Sclerosis

1 INTRODUCTION

This Statistical Analysis Plan (SAP) describes the analyses and presentation of the primary, secondary and exploratory efficacy endpoints as well as all safety, quality of life (QOL), pharmacoeconomic and pharmacodynamic (PD) endpoints for the clinical study report (CSR) of the AC-058B301 study (OPTIMUM).

Separate SAPs (not described here) are developed for analyses on:

- Pharmacokinetic (PK) endpoints
- Patient preference questionnaire
- MRI sub-study endpoints

Source data for the analyses are provided as Statistical Analysis Software (SAS[®]) data sets according to Clinical Data Interchange Standards Consortium (CDISC) Study Data Tabulation Model (SDTM).

2 STUDY DESIGN AND FLOW

The study is a prospective, multicenter, randomized, double-blind, active-controlled, parallel-group, Phase 3, superiority study in adult subjects with relapsing forms of MS. 1133 subjects are randomized in two groups: ponesimod 20 mg or teriflunomide 14 mg, using a 1:1 ratio, stratified by use of multiple sclerosis (MS) disease-modifying treatment in the last two years prior to randomization (yes, no) and by baseline Expanded Disability Status Scale (EDSS) score ($EDSS \leq 3.5$, $EDSS > 3.5$).

The study is conducted at approximately 161 sites (randomized subjects) in 28 countries in North America, Eastern and Western Europe, and Pacific region.

[figure not shown]
2.1 Study design

The overall design of the two-arm study is shown in [Figure 1](#).

Subjects who have completed treatment up to Week 108 can be enrolled in a long-term open-label extension study with ponesimod, protocol AC-058B303 (OPTIMUM-LT). Data from the extension study will not be included in the analyses described in this SAP.

Subjects who prematurely discontinue treatment can remain in the study up to Week 108, in a post-treatment observation period (PTOP).

Figure 1 Study Design

D = day; EOS = End-of-Study; EOT = End-of-Treatment; FU = follow-up; M = month; o.d. = once daily; V = visit; W = week.

2.1.1 Periods

The study consists of the following protocol defined periods:

- **Pre-randomization period** starts with signature of the Informed Consent Form (ICF) and ends with subject's randomization and lasts up to 45 days (per screening attempt). Subjects can be re-screened once.
- **Treatment period** starts on the day of randomization immediately after the 1st dose of study drug intake (Visit 3–Day 1 of the study) and continues until the premature discontinuation of study drug or the scheduled End-of-Treatment (EOT) visit at Week 108. Subjects receive double-blind treatment throughout the treatment period. The treatment period consists of a titration and a maintenance phase.
 - A 2-week titration scheme is implemented on Day 1 (or at re-initiation following a treatment interruption of more than 3 days) to reduce the first-dose effect of ponesimod [see [Table 1](#)].
 - The titration phase is followed by the maintenance phase with one capsule of ponesimod 20 mg or teriflunomide 14 mg administered orally once daily in the morning (from Day 15 to End-of-Treatment [EOT]).

- **Post-treatment period** starts immediately after the last dose of study drug and ends with the End-of-Study visit. It comprises the post-treatment safety follow-up (FU) period and if applicable, the PTOp. During the post-treatment period, all subjects undergo the accelerated elimination procedure of teriflunomide lasting for 11 days with administration of cholestyramine (8 mg three times daily, or if not tolerated 4 mg three times daily) or activated charcoal (50 g two times daily), see protocol for details.
 - **Post-treatment safety follow-up period**
For subjects who enter the extension study AC-058B303, the safety FU period ends with the FU1 visit (scheduled 14–22 days after last dose of study drug). If they have not complied with the teriflunomide accelerated elimination procedure at the time of FU1, it ends with the abbreviated FU2 visit (scheduled 23–37 days after the last dose of study drug).

For subjects who do not enter the extension study, the safety FU period ends with FU2 visit (scheduled 30–37 days after last dose of study drug).
 - **Post-treatment observation period**
Subjects who prematurely discontinue study treatment enter the PTOp period. It lasts from last dose of study drug until 108 weeks after randomization (i.e., end of planned treatment period) with 12-weekly visits as per the original visit schedule. Safety follow-up visits are conducted in addition, following the post-treatment safety follow-up period schedule.

Table 1 Dosing scheme

Treatment period	Duration	Dose regimen in the ponesimod group	Dose regimen in the teriflunomide group
Titration	Day 1 and 2	2 mg	14 mg
Titration	Day 3 and 4	3 mg	14 mg
Titration	Day 5 and 6	4 mg	14 mg
Titration	Day 7	5 mg	14 mg
Titration	Day 8	6 mg	14 mg
Titration	Day 9	7 mg	14 mg
Titration	Day 10	8 mg	14 mg
Titration	Day 11	9 mg	14 mg
Titration	Day 12 to 14	10 mg	14 mg
Maintenance	Day 15 until EOT*	20 mg	14 mg

*Visit 4 is to take place at Day 15 ± 1 day. The titration kit will therefore include an additional capsule and tablet (if applicable) for treatment on Day 15 (i.e., dose regimen in the ponesimod group = 10 mg). Dosing scheme during re-initiation following treatment interruption of > 3 days follows the same titration dosing scheme.
EOT = End-of-Treatment.

2.1.2 Blinding

This study is performed in a double-blind fashion. Refer to the protocol for aspects related to study drug material related blinding and functional blinding. To maintain functional blinding data are collected in two databases, i.e., a main database and a database with data considered to possibly lead to unblinding of treatment allocation (database of unblinding potential). During the conduct of the study, the Actelion trial team only has access to the main database. The main database will contain all data except data collected on the day of the first dose or on the day of re-initiation until discharge of the subject for: adverse events, hourly vital signs and electrocardiogram (ECG) measurements, and will exclude all post-baseline data for the lymphocytes and white-blood-cell laboratory parameters. Spirometry data will not be available to Actelion Biostatistics. Final analyses for the CSR described in this SAP will be presented from both main and first-dose databases combined.

2.2 Study visit and assessment schedule

[Table 2–Table 3](#) show a schematic representation of the assessments during the study. [Table 4](#) shows a schematic representation of the assessments during the PTOP.

Table 2 Visit and assessment schedule (Part 1)

Periods	Name	PRE-RANDOMIZATION		TREATMENT PERIOD						
	Duration	Up to 45 Days		108 Weeks						
Visits	Number	1	2	3	4	5	6	7	8-9	10
	Name	Screening	Baseline	Rand	W2	W4	W12	W24	W36 – 48	W60
	Time	Day –45 to –1		Day 1	Day 15	Week 4	Week 12	Week 24	Week 36 – 48	██████████
	Visit window				± 1 day	± 3 days	± 7 days	± 7 days	± 7 days	± 7 days
Informed consent*		X								
Inclusion/exclusion criteria*		X	X	X						
Demographics*, MS history & treatment*, McDonald criteria (revision 2010), Chest X-ray*, Tuberculosis test / Viral serology **		X								
Additional serum sample for viral serology			X							
Medical history / smoking status*		X	X							
EDSS/FS*		X	X				X	X	X	X
Relapse*			X		X <-----> X					
██████████*		X	X	X			X	X		X
FSIQ-RMS** (1), ██████████ SF-36v2**, WPAI:MS**			X				X	X		X
Health care resource utilization*					X	X	X	X	X	X
Patient preference questionnaire** (Sub-study)		X	X							
eC-SSRS**			X							X
MRI** (3)			X							X
Physical examination*		X	X			X	X	X		X
Dermatological examination*			X							X
Body weight and height* (4)		X								X
Body temperature*		X	X	X	X	X	X	X	X	X
SBP/DBP*		X	X	X(5)	X	X	X	X	X	X
12-lead ECG**		X	X	X(5)	X	X	X(6)	X	X	X
Ophthalmological examination* / OCT*		X					X	X		X
PFT incl. spirometry (All) and DL _{CO} (sub-study)**			X			X	X			X
Hematology/Chemistry** (fasted)		X	X		X	X (7) <-----> X (7)			X	X
Urinalysis		X				X	X	X		X
Pregnancy test*/**		X	X		X	X	X	X	X	X
PK sampling for ponesimod* (8)				X			X			X
Study drug dispensing & accountability */**				X	X	X	X	X	X	X
Study drug swallowing test (optional)			X							
AEs*/SAEs, Concomitant medications*		X	X	X	X	X	X	X	X	X

*Data collected in the eCRF, **Data electronically transferred to sponsor, Day 1 (date of randomization visit).
 (1) FSIQ-RMS symptoms scale will be completed for 7 consecutive days. (2) No ██████████ assessment at Baseline. (3) Non-conventional ██████████ (██████████) at selected sites only. (4) Height only at Visit 1 (Screening). (5) Pre-dose and hourly for at least 4 h post-dose and up to 12 h. (6) Pre-dose and 3 h post-dose. (7) In addition, ALT, AST, INR, alkaline phosphatase and total bilirubin at Weeks 6, 8, 10, 14, 16, 18, 20, and, 22; total white blood cell and total lymphocyte counts at Weeks 8, 16, and 20.
 (8) Pharmacokinetic sampling pre-dose at Weeks 12, 60 and 108, and 3 h post-dose on Day 1 and Week 12.

Table 3 Visit and assessment schedule (Part 2)

Periods	Name	TREATMENT PERIOD				FOLLOW-UP		UNSCHEDULED			
	Duration	108 Weeks				30 Days					
Visits	Number	11	12	13	14	15	16	R1, R2, ...	U1, U2, ...	I1, I2, ...	
	Name	W72	W84	W96	EOT	FU1	FU2	Relapse	Unscheduled (1)	Re-initiation	
	Time	Week 72	Week 84	Week 96	Week 108 or at premature discontinuation	Last study drug intake +15 days	Last study drug intake +30 days	Any day between Day 1 and EOS			
	Visit window	± 7 days	± 7 days	± 7 days	± 7 days	-1 day, +7days	+7 days (22)	+7 days	NA	NA	± 1 day
EDSS/FS*		X	X	X	X		X	X	X		
Relapse*		X<----->X				X	X	X	X		
FSIQ-RMS**			X		X			X	X		
SF-36v2**			X		X			X			
Health care resource utilization*		X	X	X	X			X			
WPAI:MS**			X		X						
(Sub-study)						X					
Chest X-ray*					X						
MRI** (2)					X				X		
eC-SSRS**					X						
Physical examination*			X		X			X	X		
Dermatological examination*, Body weight *					X				X		
SBP/DBP*, 12-lead ECG**		X	X	X	X	X	X	X	X	X(3)	X
Pulse rate*								X	X(4)		
Ophthalmological examination / OCT*					X				X		
PFT incl. spirometry (All) and DL _{CO} (sub-study)**					X	X	X		X		
Hematology/Chemistry**(fasted)		X	X	X	X	X	X		X		
Urinalysis			X		X	X			X		
Viral serology, Serum sample vaccination*									X		
Pregnancy test*/**		X	X	X	X	X	X		X		
PK sampling for ponesimod*					X				X(5)		
Teriflunomide plasma concentration									X(4)		
Accelerated elimination procedure					X	X(4)					
Accelerated elimination procedure compliance						X	X(4)				
Study drug dispensing/accountability		X	X	X	X			X	X	X	X
AEs*/SAEs, Concomitant medications*, Body temperature*		X	X	X	X	X	X	X	X	X	X

*Data collected in the eCRF, **Electronically transferred to sponsor, Day 1 = date of randomization visit,

(1) Unscheduled visits may include all or some of the indicated assessments. (2) Brain MRI to be performed at any time an opportunistic infection in the CNS is suspected.

Non-conventional [redacted] at selected sites only. Note: MRI assessment at EOT does not need to be performed if the EOT visit occurs within < 4 weeks of the MRI assessment at Visit 10. (3) Pre-dose and hourly for at least 4 h post-dose and up to 12 h. (4) If needed (see protocol for details). (5) When possible, collect PK sample upon experiencing SAE.

Table 4 Visit and assessment schedule (Part 3)

Periods	Name	POST-TREATMENT OBSERVATION PERIOD (PTOP) (to be performed after EOT)		
	Duration	Up to 108 Weeks		
Visits	Number	6A, 8A, 9A, 11A,13A	7A, 12A	10A, 14A
	Name	W12A, W36A, W48A, W72A, W96A	W24A, W84A	W60A, W108A
	Time	Week 12-36-48-72-96	Week 24 and 84	Week 60 and 108
	Visit window	±7 days	±7 days	±7 days
EDSS/FS*	X	X		X
Relapse*		X<----->X		
MRI*				X
FSIQ-RMS** (1), [REDACTED]**, [REDACTED]*	X (only Week12)	X		X
Concomitant medications*	X	X		X
Physical examination*				X
Dermatological examination*				X
SBP/DBP*	X	X		X
12-lead ECG **				X
Body temperature*	X	X		X
PFT incl. spirometry (All) and DL _{CO} (sub-study)**				X (Week 108 only)
Hematology/Chemistry** (fasted)		X		X
Urinalysis*		X		X
Pregnancy test*/**	X	X		X
AEs/SAEs *	X	X		X

*Data collected in the eCRF, **Electronically transferred to sponsor, Day 1 = randomization visit. If the first PTOP visit windows overlaps with FU1 or FU2 visits, visits and assessments can be combined.

AE = adverse event; ALT = alanine aminotransferase; AST = aspartate aminotransferase; [REDACTED]; CNS = central nervous system; d = day(s); DBP = diastolic blood pressure; DLco = Diffusing capacity for carbon monoxide; [REDACTED]; ECG = electrocardiogram; eCRF = electronic case report form; eC-SSRS = Columbia Suicide Severity Rating Scale (electronic self-rated version); EDSS = Expanded Disability Status Scale; EOS = End of Study; EOT = End of Trial; FS = functional system; FSIQ-RMS = Fatigue Symptom and Impact Questionnaire-Relapsing Multiple Sclerosis; FU = Follow-up; h = hour(s); INR = international normalized ratio; MRI = magnetic resonance imaging; MS = multiple sclerosis; MTR = magnetization transfer ratio; OCT = Optical coherence tomography; PFT = pulmonary function test; [REDACTED]; severity; PK = pharmacokinetic(s); SAE = serious adverse event; SBP = systolic blood pressure; [REDACTED] test; W = week(s); WPAI:MS = Work Productivity Activity Impairment: Multiple Sclerosis.

3 OBJECTIVES

3.1 Primary objective(s)

The primary objective of the study is to determine whether ponesimod is more efficacious than teriflunomide in terms of reducing relapses in subjects with Relapsing Multiple Sclerosis (RMS).

3.2 Secondary objectives

- To assess the effect of ponesimod on disability accumulation and on other aspects of MS disease control;
- To assess the safety and tolerability of ponesimod in subjects with RMS.

4 CHANGES OR CLARIFICATIONS TO ANALYSES PLANNED IN THE STUDY PROTOCOL

4.1 Changes to the analyses planned in the study protocol

Sensitivity analyses of the primary endpoints related to early study withdrawal as specified in section 11.3.2.2.2 of the protocol have been updated to account for recent advancements in statistical methodology by applying multiple imputation (MI) techniques for negative binomial count data [see Section 9.6.4.3].

The assumptions for the multiple imputation approaches for imputation of relapses between EOS and Week 108 following premature study withdrawal are generally in line with those specified in the protocol.

An overview of the newly introduced multiple imputation approaches is provided below:

Protocol approach	SAP approach
Impute with the observed individual treatment ARR	'Missing at Random' approach: ARR after withdrawal for each treatment arm is assumed to be the ARR in the respective arm before withdrawal. Equivalent to protocol specified approach.
Impute with the observed teriflunomide ARR for both treatment arms	Reference-based MI approaches: The rate in the reference (teriflunomide) arm is used for imputation in both the ponesimod and teriflunomide arms. Two different approaches, 'Copy reference' and 'Jump to reference', are applied, see Section 9.6.4.3 for details. Similar to protocol specified approach.

Impute with the observed ARR for 'Delta adjustment' MI approach: A range of deltas (deviation from ponesimod and impute zero relapses the MAR assumption based on multiplicative factors δ for ARR) for teriflunomide covering plausible to extreme and unlikely scenarios are considered for both treatment arms.

The scenario with $\delta = 0.1$ for teriflunomide (impute based on $0.1 \times$ teriflunomide ARR under MAR) and $\delta = 1$ for ponesimod (impute based on ponesimod ARR under MAR) represents a scenario that is similar, but slightly less extreme than the protocol specified approach. The equivalent delta adjustment scenario to the protocol approach ($\delta = 0$ for teriflunomide) is not considered to avoid numerical instabilities of the multiple imputation algorithm.

For the imputation analyses after EOT + 7 days (see sensitivity analyses in Section 9.6.5.1) the period for imputing relapses is from EOT + 7 days to Week 108 in the SAP instead of from EOT + 7 days to EOS as specified in section 11.3.2.4 of the protocol. Rationale for the change is to align with the per protocol planned period for observing relapses at least up to Week 108 and to handle intercurrent events of premature treatment discontinuation irrespective of subsequent study withdrawal. Purpose of the analysis remains to assess the impact of treatment discontinuation and/or switching to alternative MS treatments as specified in the protocol.

4.2 Changes in the conduct of the study / data collection

A total of 6 protocol amendments were conducted. The main reasons are described below.

Protocol version 2, 29 April 2015: Addition of a sub-study assessing patient preferences for different outcomes in the treatment of multiple sclerosis.

Protocol version 3, 16 July 2015: Among other changes, the following updates were made to address comments received after Voluntary Harmonization Procedure review for this Clinical Trial Application in the EU: Introduction of the electronic self-rated version of the Columbia-Suicide Severity Rating Scale (eC-SSRS), total white blood cell and total lymphocyte count monitoring every four weeks up to Week 24; Reducing the time window for the EDSS assessments to ensure that EDSS assessments of two subsequent visits are at least 10 weeks and no more than 14 weeks apart.

Protocol version 4, 5 February 2016: Addressing a comment received from the US FDA regarding the assessment of relapses. For this purpose, a standardized step-wise procedure for the early detection, confirmation and reporting of relapses has been introduced. This included incorporating a relapse assessment questionnaire into the study (based on telephone calls and visits).

Protocol version 5, 14 November 2016 Main reason for the amendment was to modify the procedure for teriflunomide plasma concentration testing after the subject's discontinuation from study treatment. Further small clarifications and updates were made.

Protocol version 6, 30 August 2017 Main reason for the amendment was to allow for testing of teriflunomide plasma concentration in any subject who has discontinued study drug if deemed necessary for the subject's safety, at the discretion of the investigator. Timing of the testing of teriflunomide plasma concentration remains dependent on study drug discontinuation and compliance with the accelerated elimination procedure. Further small clarifications and updates were made.

Protocol version 7, 5 Dec 2018 Changes include updating the testing strategy for the secondary endpoints from a hierarchical testing strategy to the described fallback type strategy. [REDACTED] are demoted from secondary to exploratory endpoints. Time to 24-week disability has been added as a secondary endpoint following CHMP feedback.

4.3 Clarifications concerning endpoint definitions and related variables or statistical methods

The protocol endpoints 'Change from baseline to EOS vs change from baseline to EOT' for lymphocyte counts, pulmonary function tests (PFTs) and DL_{CO} parameters analyses for assessing reversibility are clarified as follows: 'Change from baseline to EOS' is clarified to not include assessments from the post-treatment observation period, but only from the safety follow-up period (up to EOT + 37 days). Consequently, in this SAP the terminology 'change from baseline to last follow-up assessment' instead of 'change from baseline to EOS' is used. The rationale for this is to allow the assessment of the reversibility of the effects on these endpoints prior to the initiation of other DMTs in the PTOP.

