5.5 Safety variables

5.5.1 Definition of treatment-emergency, baseline and change-from-baseline, last on treatment, follow-up assessments for safety variables

For all safety data analyses described in this SAP, baseline is considered to be the last valid assessment prior to first study drug intake.

For each individual safety variable, baseline is defined to be the last valid measurement available before the date and time of first dose intake of study treatment, unless otherwise specified. On days where study drug is initiated or re-initiated, the pre-dose assessment for that day is defined as the last non-missing assessment prior to the study drug intake on that day. The pre-dose assessment on Day 1 (if available) is identical to baseline; however, missing pre-dose data on Day 1 is not imputed with baseline. In case of (partially) missing assessment dates/times, or for assessments reported on Day 1 (or day of re-initiation) with recorded assessment time contradicting the time point label (e.g., pre-dose, 2 hours post-dose), the nominal visit and time point labels will be used to determine whether an assessment is considered for baseline (for example a blood pressure measurement with an assessment date on Day 1 but with a missing assessment time or an assessment time prior to the reported time of first study drug intake, will not be considered for baseline if reported under the time-point “2 hours post-dose” in the eCRF, however it will be considered if reported as “Pre-dose” in the eCRF).

Absolute changes from baseline are defined as post-baseline value minus baseline value, i.e., a positive sign indicates an increase compared to baseline.

A percentage change from baseline is defined as the absolute change from baseline divided by the baseline value (if the baseline value is > 0) and then multiplied by 100.

Absolute and percent change from baseline is calculated and stored for all continuous safety data.

In addition, the following assessments are flagged or derived per parameter:

- Last on-treatment assessment: Last assessment prior to or on EOT date +1 day)
- Day-15 follow-up, between EOT + 8 days and EOT + 22 days [see Section 11.4]
- Day-30 follow-up, between EOT + 23 days and EOT + 37 days [see Section 11.4]
- Last follow-up assessment: Last assessment between EOT + 8 and EOT + 37 days

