9.4.5.1 Disease modifying therapies (DMTs) for MS

The following therapies are summarized in the same way as for the previous / concomitant therapies above by treatment group and overall on the FAS:

- Previous DMTs for MS
- Study concomitant DMTs for MS
- Treatment concomitant DMTs for MS
- DMTs for MS started after EOT + 7 days

All DMTs for MS taken are reported in one subject listing using flags to mark previous, study concomitant, treatment concomitant as well as ongoing at study treatment start using the FAS.

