9.13 Analysis of pharmacodynamic variables

Descriptive analyses of lymphocyte data are described in Section 9.10.5. Only lymphocyte counts from central laboratory, irrespective of whether obtained at a scheduled or unscheduled visit, are included in any of the below describe analyses.

For each subject in the SAF, the

- Nadir (i.e., lowest) treatment-emergent lymphocyte value (up to EOT + 15 days)

is identified and summarized by means of frequency counts and percentages based on the categories specified in Section 5.8.

Lymphocyte counts and percent change from baseline in lymphocyte counts at the following time points [for definition, see Section 5.8] are summarized using descriptive

statistics and displayed graphically by box-and-whisker plots visualizing mean, median, interquartile ranges, SD, and outliers over time: Baseline, Last on-treatment, Day-15 follow-up (plus one display adding Day-30 follow-up in addition). Only subjects with data available at all three (four) time points are included. Corresponding descriptive data is tabulated.

Individual absolute and percent change from baseline in lymphocyte counts to last assessment on treatment versus absolute and percent change from baseline to last follow-up is graphically presented by means of scatterplots with treatment groups color-coded.

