11.4 Summaries by visit

Visit based safety and PD assessments are generally summarized according to the nominal visit. Except for Visit 14 (EOT/Week 108) in subjects prematurely discontinuing study treatment, Visit 15 (FU1, Day-15 follow-up assessment), and Visit 16 (FU2, Day-30 follow-up assessment). Those are derived following the rules below:

- Premature EOT visits are re-assigned following the visit windowing described in Section 11.3
- Day-15 follow-up assessment: Any assessment within EOT date + 8 days and EOT date + 22 days. If multiple assessments fall into that period, the one corresponding to the regular FU1 visit (Visit 15) is selected, if none of the multiple assessments corresponds to that visit, the one closest to EOT date +15 days is selected, if there are two closest assessments, the later one is selected.
- Day-30 follow-up assessment: Any assessment within EOT date + 23 days and EOT date + 37 days. If multiple assessments fall into that period, the one corresponding to the regular FU2 visit (Visit 16) is selected, if none of the multiple assessments corresponds to that visit, the one closest to EOT date + 30 days is selected, if there are two closest assessments, the later one is selected.

In addition, the ‘Last on-treatment’ assessment is flagged. This is defined to be the latest assessment prior to or on EOT date +1 day.

Summaries by visit are presented by Baseline (derived), and further scheduled nominal visits up to Week 108 (irrespective if conducted during PTOP or not), Last on-treatment, and derived Follow-up visits (FU1, FU2). Generally, by visit tables are tabulating the baseline and nominal and derived visits as follows:

- Baseline (Note: This is not a nominal visit but the derived baseline; see Section 5.5.1)
- Visit 4 - Week 2

- Visit 5 - Week 4
- Visit 6 - Week 12
- Visit 7 - Week 24
- Visit 8 - Week 36
- Visit 9 - Week 48
- Visit 10 - Week 60
- Visit 11 - Week 72
- Visit 12 - Week 84
- Visit 13 - Week 96
- Visit 14 - Week 108
- Last on-treatment (derived; see Section 5.5.1)
- Day-15 follow-up (derived)
- Day-30 follow-up (derived)

Premature EOT visits are mapped to and summarized within a scheduled visit following the window approach described in Section 11.3; they will not be summarized as “Visit 14 - Week 108” unless they are mapped to this visit as per approach described in Section 11.3.

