3.1. Safety

Condition	Type	Identifier	Source/Instructions	Additional information expected?	Important PD
Procedure for accelerated elimination of teriflunomide not followed	M	PD_MM.079	eCRF / Monitor PD / e.g.: not done, duration < 7 days, doses < 21, compliance not assessed or assessed as not sufficient for subjects participating to the extension study		No
Any safety follow-up assessment not done or done after first study drug intake in OPTIMUM-LT	M	PD_MM.205	eCRF / Monitor PD / Valid for Visit 14-16 assessments including: Physical examination, Body weight, both Ophthalmological examination and OCT, Body temperature, SBP/DBP, Spirometry, Hematology, Chemistry, Urinalysis, Pregnancy test, ec-SSRS		No

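### The follow-up windows used to judge reversibility end on a calendar day, not at the start of a new DMT, so they do not ensure the purpose stated in SAP Section 4.3

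*SAP*

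**What the plan says.** Section 4.3 redefines the follow-up value for lymphocytes, pulmonary function tests and DLCO. Post-treatment observation period (PTOP) assessments are left out and data are taken "but only from the safety follow-up period (up to EOT + 37 days"). The reason given is "to allow the assessment of the reversibility of the effects on these endpoints prior to the initiation of other DMTs in the PTOP".

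The working definitions are these:

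- Section 5.5.1: "Last follow-up assessment: Last assessment between EOT + 8 and EOT + 37 days".
- Section 11.4, Day-15 follow-up: "Any assessment within EOT date + 8 days and EOT date + 22 days".
- Section 11.4, Day-30 follow-up: "Any assessment within EOT date + 23 days and EOT date + 37 days".
- Section 5.8 applies the same rules to lymphocyte counts.

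These values feed the box plots and scatterplots in Sections 9.10.6 (spirometry), 9.10.7 (DLCO) and 9.13 (lymphocytes), and the spirometry reversibility table. For lymphocytes the box-plot time points are "Baseline, Last on-treatment, Day-15 follow-up (plus one display adding Day-30 follow-up in addition"). None of these sections mentions the start of another DMT.

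**The concern.** The stated aim is to see whether an effect wears off once study drug stops and before another MS drug is given. A day limit serves that aim only if nobody switches before the limit. A lymphocyte count taken after a switch to a lymphocyte-lowering drug carries no information about recovery from ponesimod, yet it would enter the displays as if it did.

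The SAP gives grounds for taking this seriously for lymphocytes. Table 5 counts fingolimod, siponimod, ozanimod, ocrelizumab and rituximab as DMTs. Section 7.1.3 gives rituximab and ocrelizumab as examples of lymphocyte-depleting agents, and names fingolimod and ponesimod together with other S1P modulators. Section 2.1.2 withholds post-baseline lymphocyte counts from the trial team because they could reveal the allocation.

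What is at stake is the reading of the descriptive reversibility displays. No hypothesis test is involved.

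**Working it through.** **1. Reproduce the window (days from EOT, both ends included).**

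- Day-15 window: 22 − 8 + 1 = 15 days.
- Day-30 window: 37 − 23 + 1 = 15 days.
- Last follow-up: 37 − 8 + 1 = 30 days = 15 + 15.

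The two windows tile the last-follow-up window and agree with the EOT + 37 limit in Section 4.3.

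**2. Can a DMT start inside it?** Setting the sections side by side:

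- Section 2.1.1: the PTOP runs from the last dose, so it overlaps the whole window.
- Table 4, footnote: the first PTOP visit may be combined with FU1 or FU2.
- Section 9.6.1: alternative DMTs are allowed only once study treatment has been discontinued. No waiting time is stated.
- Section 5.2.5.4: therapies count as starting after EOT from EOT + 1 day.

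Nothing in the SAP keeps a DMT start out of days 8 to 37.

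**3. How much of the window stays open after a start?** The start day *s* is not in the SAP, so it is an assumption shown as a range. Eligible days on or after the start = 30 if *s* ≤ 8, otherwise 38 − *s*.

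| Assumed start | Eligible days on or after start |
|---|---|
| EOT + 1 | 30 of 30 |
| EOT + 8 | 30 of 30 |
| EOT + 12 | 26 of 30 |
| EOT + 15 | 23 of 30 |
| EOT + 23 | 15 of 30 |
| EOT + 30 | 8 of 30 |

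The visits cluster within the window: FU1 at days 14–22 and full FU2 at days 30–37 (Section 2.1.1). With both visits on schedule, a start before day 14 precedes both, and a start on days 23–29 precedes only FU2. The last-follow-up rule takes the latest sample, the one most likely to follow a switch.

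**4. Which displays can be affected, and how?**

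- *Lymphocytes (9.13) and DLCO (9.10.7):* descriptive statistics and plots, with no recovered or not recovered category. If a fraction *f* of displayed subjects have switched and their counts are lower by *d* on average, the mean shifts by *f* × *d*. The SAP gives neither quantity.
- *Lymphocyte display with Day-30 added:* it needs data at all four time points. Extension entrants normally finish at FU1 (Section 2.1.1), so it rests mainly on subjects who do not enter the extension, including early discontinuers.
- *Spirometry (5.5.13.1):* the only classification. Entry to the subset needs a fall of at least 200 mL **or** at least 12%; not reversible needs **both**. An unchanged fall of 0.25 L from 3.0 L (0.25 / 3.0 = 8.3%) enters the subset and is labelled reversible.

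**5. Open-label ponesimod.** Section 2.1 excludes extension data, and Section 5.4.1 schedules EOS before extension entry. What remains is deviation PD_MM.205, "Any safety follow-up assessment not done or done after first study drug intake in OPTIMUM-LT". It covers core-study hematology and spirometry at Visits 14–16 and is rated not important. The SAP gives no rule to drop such values.

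**6. Does the SAP use such a cut elsewhere?** Yes. Section 5.4.1.2.5 stops one ARR variable the day before a new DMT starts. Its date is the first start of any study concomitant DMT (Section 5.2.5.5), which can precede EOT, so it is not the date needed here.

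**The case against.** The strongest reply is that Section 4.3 claims only to allow the assessment, and that moving from EOS, which can lie as late as Week 108 in the PTOP, to EOT + 37 removes most post-switch time. The protocol, which is not at hand, may impose a waiting time. When several assessments fall in a window, Section 11.4 prefers the regular follow-up visit. DMTs and laboratory, spirometry and DLCO results are all listed by subject.

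Much of this stands as a limit on size. It does not close the gap: the regular visit can itself follow a switch, and listings do not correct a summary or plot.

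Four stronger readings are tempting, and the SAP does not support them.

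- *Post-switch values are read as failure to recover.* Only FEV1 and FVC have such a label, and its rule leans towards reversible. The SAP gives no mechanism by which another DMT would lower lung function.
- *Early switches are expected.* The planned table of "DMTs for MS started after EOT + 7 days" has no upper limit and runs through the PTOP, so it says nothing about days 8–37 in particular.
- *Open-label ponesimod broadly contaminates the windows.* The exposure is confined to PD_MM.205 cases, and a deviation code does not show that any occurred.
- *A number of affected subjects can be given.* The SAP has 1133 randomized subjects and 333 in the DLCO subset, but no rate of early discontinuation or early switching.

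**Conclusion.** The point holds as a mismatch between a stated purpose and the rule that implements it. The windows do not ensure that reversibility is assessed before another DMT starts, and samples taken after a switch can enter the displays. The practical exposure is mainly lymphocyte counts after a lymphocyte-lowering DMT, with the Day-30 display the most exposed. The effect would be shifted descriptive summaries and plots, of unknown size.

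This rests on the SAP stating no waiting time between EOT and a new DMT. If the protocol sets one, the exposure shrinks accordingly. It is worth correcting because reversibility is a named endpoint and the repair is small.

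**What to change.** In Sections 5.5.1, 5.8 and 11.4, for the lymphocyte, spirometry and DLCO reversibility displays:

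1. Use only follow-up assessments dated before the first DMT that starts after EOT, meaning a therapy with a start date from EOT + 1 day (Section 5.2.5.4). Do not reuse the date in Section 5.4.1.2.5.
2. State how partial DMT start dates are handled. Section 12.1.1 imputes them to the lower limit, no earlier than treatment start. A start known only to be in the month of EOT could then be placed before EOT and trigger no cut, while one in the next month could remove a valid sample. Missing start dates are not imputed and need a stated rule as well.
3. Drop PD_MM.205 assessments done after the first OPTIMUM-LT dose.
4. List the excluded values by treatment arm.

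The cost is one date condition in the SAP and programs. DMT dates are already collected; the first extension dose date is needed only for PD_MM.205 cases. A few subjects lose a follow-up value, and so may drop out of displays that require every time point.
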